11 questions are included in the Emotional Well-Being score. Question 21 (IDLEMO12) is excluded from calculation. If 50% (5) or fewer of the 11 questions used in the calculation of Emotional Well-Being score have missing item score, then the scale score is calculated by multiplying the mean of the non missing item scores by 25. If 6 or more of the 11 item scores are missing then the scale score is not calculated and should be set at missing. Multiplying by 25 transforms

Confidential

the scale score to a 0 to 100 scale, with 0 reflecting the worst level of emotional well-being measurable by the scale and 100 reflecting the best.

1.c Work

| Work | Used in calculation of domain score? |
|--|--|
| 22. Are you currently working? | - |
| 23. Feeling distracted | Yes |
| 24. Feeling like I couldn't concentrate | Yes |
| 25. Having to take a break from work | Yes |
| 26. Having to change the way I work (such as the way I read, look at a computer, or work outside) | Yes |
| 27. Having to change my work environment (such as how close I am to an air conditioning or heating vent) | Yes |

| Response for question 22 | Original response code | Item score |
|--------------------------|---------------------------|------------|
| Yes | 1 | 1 |
| No | 2 | 0 |

| Response for questions 23 to 27 | Original response code | Item score If Response for question 22=0 | Item score If Response for question 22=1 |
|---------------------------------|------------------------------|--|--|
| None of the time | 1 | Missing | 4 |
| A little of the time | 2 | Missing | 3 |
| Some of the time | 3 | Missing | 2 |
| Most of the time | 4 | Missing | 1 |
| All of the time | 5 | Missing | 0 |

5 questions are included in the Work Limitations domain. If 50% (2) or fewer of the 5 questions used in the calculation of the Work Limitations score have missing item scores, then the scale score is calculated by multiplying the mean of the non missing item scores by 25. If 3 or more of the 5 item scores are missing then the scale score is not calculated and should be set to missing. Multiplying by 25 transforms the scale score to a 0 to 100 scale, with 0 reflecting the greatest degree of limitation at work measurable by the scale and 100 reflecting the least limitation at work.

Module 2:

Confidential Final Version 1.0, 2021-05-20 Dry eye Treatment satisfaction & Bother module (10 questions) comprising 2 QoL domains: 2.a "Treatment satisfaction / Happiness" and 2.b "Treatment-related bother".

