2.a Treatment - In general

| Treatment in General | Used in calculation of domain score? |
|--|--|
| 1. OVER THE LAST TWO WEEKS, how often did you use | - |
| treatment for your dry eyes? | |
| 2. I was happy with how quickly my treatments worked | Yes |
| 3. I was happy with how long the effects of my | Yes |
| treatments lasted | |
| 4. The treatments I used completely eliminated my dry | Yes |
| eye symptoms | |
| 5. The treatments I used relieved most of my dry eye | Yes |
| symptoms | |
| 6. I was bothered by how often I had to use dry eye | Yes |
| treatments | |

| Response for question 1 | Original response code | Item score |
|-------------------------|------------------------------|------------|
| None of the time | 1 | 0 |
| A little of the time | 2 | 1 |
| Some of the time | 3 | 2 |
| Most of the time | 4 | 3 |
| All of the time | 5 | 4 |

| Response for questions 2 to 5 | Original response code | Item score If Response for question 1 = 0 | Item score If Response for question 1 > 0 or missing |
|----------------------------------|------------------------------|---|---|
| None of the time | 1 | Missing | 0 |
| A little of the time | 2 | Missing | 1 |
| Some of the time | 3 | Missing | 2 |
| Most of the time | 4 | Missing | 3 |
| All of the time | 5 | Missing | 4 |
| Response for question 6 | | | |
| None of the time | 1 | Missing | 4 |
| A little of the time | 2 | Missing | 3 |
| Some of the time | 3 | Missing | 2 |
| Most of the time | 4 | Missing | 1 |

Confidential

Final Version 1.0, 2021-05-20

Statistical Analysis Plan

| All of the time | 5 | Missing | 0 |
|-----------------|---|---------|---|

5 questions are included in the Treatment Satisfaction/Happiness scale score. If 50% (2) or fewer of the 5 questions used in the calculation of Treatment Satisfaction/Happiness score have missing item score, then the scale score is calculated by multiplying the mean of the non missing item score by 25. If 3 or more of the 5 item scores are missing then the scale score is not calculated and should be missing. Multiplying by 25 transform the scale score to a 0 to 100 scale, with 0 reflecting the lowest level of satisfaction/happiness with treatment measurable by the scale and 100 reflecting the highest level of satisfaction/happiness with treatment.

2.b Treatment- Eye Drops

| Treatment- Eye Drops | Used in calculation of domain score? |
|--|--|
| 7. Do you ever use eye drops to treat your dry eyes? | - |

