| 8. I was bothered by blurriness shortly after using my eye | Yes |
| drops | |
| 9. I was embarrassed when I had to use my eye drops | Yes |
| 10. I felt like I could not go anywhere without my eye drops | Yes |

| Response for question 7 | Original response code | Item score |
|-------------------------|---------------------------|------------|
| Yes | 1 | 1 |
| No | 2 | 0 |

| Response for question 8 to 10 | Original response code | Item score If Response for question 1 = 0 | Item score If Response for question 1 > 0 |
|----------------------------------|------------------------------|---|---|
| None of the time | 1 | Missing | 4 |
| A little of the time | 2 | Missing | 3 |
| Some of the time | 3 | Missing | 2 |
| Most of the time | 4 | Missing | 1 |
| All of the time | 5 | Missing | 0 |

3 questions are included in the Treatment-Related Bother scale score. If 50% (1) or fewer of the 3 questions used in the calculation of Treatment-Related Bother scale score have missing item scores, then the scale score is calculated by multiplying the mean of the non missing item score by 25. If 2 or more of the 3 item scores are missing then the scale score is not calculated and should be set at missing. Multiplying by 25 transforms the scale score to a 0 to 100 scale, with 0 reflecting the greatest degree of treatment related bother measurable by the scale and 100 reflecting the lowest degree of treatment-related bother.

Confidential

Final Version 1.0, 2021-05-20

Module 3:

Dry eye Symptom bother (20 questions) comprising a unique domain.

| Symptom Bother | Used in calculation of domain score? |
|---|--|
| 1.OVER THE LAST TWO WEEKS, how often did you | Yes |
| experience dry eye symptoms? | |
| 2. Eyes that felt gritty or sandy | Yes |
| 3. Felt like I needed to close my eyes even though I was not | Yes |
| tired | |
| 4. Burning or stinging eyes | Yes |
| 5. Tired eyes | Yes |
| 6. Blurry vision | Yes |
| 7. Itchy eyes | Yes |
| 8. Irritated eyes | Yes |
| 9. Eyes that felt like they had been scratched by something | Yes |
| 10. Eye dryness | Yes |
| 11. Mucus in, around, or coming out of my eyes | Yes |
| 12. Puffy or swollen eyes | Yes |
| 13. Eye redness | Yes |
| 14. Aching or sore eyes | Yes |
| 15. Felt like something was in my eye | Yes |
| 16. Frequent and/or rapid blinking | Yes |
| 17. Difficulty blinking because of little or no moisture in my eyes | Yes |
| 18. Sensitivity to light, glare, and/or wind | Yes |

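### IDEEL Module 2.b codes question 7 (ever uses eye drops) as a filter but never uses it; items 8–10 are gated on question 1 instead, with no rule when question 1 is blank

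*SAP*

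**What the plan says.** SAP 5.2 (Secondary Efficacy Variables) sets out the item-level scoring of the IDEEL. Three blocks contain conditional items.

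- **Block 1.c, Work.** Question 22 (currently working, Yes = 1, No = 0) is not part of the domain score. It decides whether items 23–27 count; the first column is headed "Item score If Response for question 22=0" and sets those items to missing.
- **Block 2.a, Treatment in general.** Question 1 ("1. OVER THE LAST TWO WEEKS, how often did you use" treatment for dry eyes) is scored 0 to 4 and is not part of the domain score. It decides whether items 2–6 count. The scoring column is headed "Item score If Response for question 1 > 0 or missing", so a blank question 1 is covered.
- **Block 2.b, Eye drops.** The block opens with "7. Do you ever use eye drops to treat your dry eyes". This item is not part of the domain score, and under "Response for question 7" it is coded Yes = 1, No = 0. The table for items 8–10 is then headed "Item score If Response for question 1 = 0" (all missing) and "Item score If Response for question 1 > 0" (scored 4 down to 0).

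The Treatment-Related Bother score is 25 times the mean of the available items. On missing items the rule is: "If 2 or more of the 3 item scores are missing then the scale score is not calculated and should be set at missing". Change from baseline in each subscore is tabulated at Weeks 4, 8 and 32 (Table 14.2.7) and shown in a radar plot (Figure 14.2.1).

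**The concern.** Question 7 is built like a filter: a yes/no item at the head of its block, kept out of the domain score and given a 0/1 code. No rule in the SAP then uses that code. The items it introduces are gated on a question from the previous block, with a different scope (any treatment, not drops) and a different time frame (two weeks, not ever). Block 1.c has the same layout and uses its own yes/no item. The 2.b header therefore looks carried over from 2.a, and without the provision for a blank answer that 2.a has.

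This is a stated derivation rule, not a gap that a programmer would query, and SAP section 1 says that the SAP supersedes the protocol's statistical considerations. It would be coded as it stands. At stake are who receives a Treatment-Related Bother score at each visit and, through the baseline value, who contributes to change from baseline in that domain.

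**Working it through.** **Inputs (all SAP 5.2, Module 2).** Question 1 is scored 0–4. Question 7 is scored 0 or 1. Items 8–10 are scored 4 (*None of the time*) to 0 (*All of the time*). Domain = 25 × mean of non-missing items, and missing if 2 or more of the 3 items are missing.

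**Scale range.** Three scores of 4 give 25 × 12/3 = 100. Three scores of 0 give 0. The SAP's 0 to 100 range is reproduced.

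**Effect of a filter.** Either filter acts on all three items together. Three missing exceeds the one that is tolerated, so a filtered patient always loses the whole domain.

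**Comparison of the two filters.** Take a patient whose answers to items 8–10 score 3, 2 and 2, so the domain is 25 × 7/3 = 58.3.

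| Question 1 | Question 7 | Question 1 filter (as written) | Question 7 filter |
|---|---|---|---|
| 0 | No | missing | missing |
| 0 | Yes | **missing** | **58.3** |
| 1–4 | No | **58.3** | **missing** |
| 1–4 | Yes | 58.3 | 58.3 |
| blank | Yes | **no rule** | **58.3** |
| blank | No | **no rule** | **missing** |

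In the third row, a patient who answers *None of the time* to all three items scores 100, the best possible value, for drops they report never using. A question 7 filter would in turn need a rule for a blank question 7.

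Patients who leave two or more of items 8–10 blank have no domain score under either filter. The choice therefore matters only for patients with discordant answers to questions 1 and 7, or a blank filter answer, who answered at least two of items 8–10.

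**When discordance is plausible.**

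- *Baseline (Visit 2).* The two-week recall of question 1 coincides with the 14-day washout, when other topical treatment stops and artificial tears are optional, up to four times a day (Protocol synopsis and 3.3). A habitual drop user who needed none could truthfully give question 1 = 0 and question 7 = Yes.
- *Weeks 4 and 8.* Patients instil six drops a day. If they count the study product as dry-eye treatment, the two filters should agree.
- *Week 32.* Tears are again used only as needed. Unhealed patients may also receive suture-less amniotic membrane (Protocol synopsis), so treatment without drops is possible.

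A missing baseline removes the patient from all three change scores for this domain. A missing Week 32 value affects Week 32 alone.

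**Leverage of one record.** If 35 patients contribute (the planned evaluable number, used here as an assumption) and one has a spurious 100, the visit mean rises by (100 − m)/35, where m is the mean of the other 34. The ceiling, at m = 0, is 100/35 = 2.9 points. At the illustrative m = 58.3 the rise is 41.7/35 = 1.2 points.

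**The case against.** The strongest reply is that the right filter is set by the IDEEL User Manual, which the SAP cites and which is not part of these documents. A reader might infer that question 7 is proven to be the instrument's filter. The documents do not show that. They show a coded item left unused and a layout that differs from block 1.c. This objection stands, and the manual has to be consulted before the header is changed.

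Second, removing the domain when question 1 = 0 may be sound. If items 8–10 share the two-week recall, which the SAP tables do not say, bother from drops does not apply to someone who used no treatment in that time. A question 7 filter could also give 100 to a patient who has used drops before but not in the fortnight. This stands for the question 1 = 0, question 7 = Yes group. It gives no support to scoring patients who say they never use drops.

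Third, that second group should be small. During washout, during treatment and, for healed patients, during follow-up, the ocular treatment allowed is essentially drops. This stands as to frequency, not as to the rule.

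Fourth, block 1.c has no rule for a blank question 22 either. That is true, so the missing-filter gap is not unique to 2.b. Still, 2.a shows that the authors meant to handle it within this module.

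**Conclusion.** The point holds as an internal inconsistency in a stated scoring rule. Question 7 is coded and unused, items 8–10 are gated on the filter of another block, and a blank question 1 has no rule. Scoring the domain for patients who report never using drops has no evident justification. Removing it for question 1 = 0 with question 7 = Yes may or may not be intended.

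The size is limited and cannot be quantified from the documents. A reader might infer that everyone who reports no treatment in the past two weeks is wrongly lost, and that the mean change is therefore selectively biased. The documents do not support this. Patients with question 1 = 0 and question 7 = No are missing under both filters, and no rate of discordance is given for the rest.

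The effect is confined to one of six IDEEL subscores, in a secondary variable that is summarised descriptively. SAP 2.10 calls all efficacy analyses exploratory, and Protocol 9.3.2 plans no formal hypothesis test. Quality of life is named in the primary objective, but the primary efficacy variable, epithelial healing at Week 8, is untouched. The correction is worth making because it is cheap and the rule would otherwise be programmed literally.

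**What to change.** Before database lock, compare the 2.b table with the IDEEL User Manual.

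- **Unless the manual specifies question 1:** change the two column headers to question 7 = 0 (items 8–10 missing) and question 7 = 1 (items 8–10 scored), and state what happens when question 7 is blank.
- **If the manual does specify question 1:** say so in the SAP, add the rule for a blank question 1, and set items 8–10 to missing when question 7 = No. If that last step is not in the manual, record it as a departure from it.

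The cost is one pair of table headers, one sentence on the missing filter answer and the matching line of derivation code. No new data are needed, since the item responses are collected anyway and the IDEEL data are listed (Listing 16.2.6.6).

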| All of the time | 6 | 1 |
| I can no longer do this activity due to my | 7 | 0 |
| dry eyes | | |

The response option "I did not do this activity for reasons other than my dry eyes" has a response coded 1 but a scored item value of 5. The original response code is the value to be used for data-entry. The item score is used during the computation of the Daily Activity Limitations Scale Score. Higher item scores are intended to reflect better quality of life (i.e. less limitations on daily activities). Only the first 6 questions are included in the Daily activity Limitations scale score. Questions 7, 8 and 9 are excluded. If 50% (3) or fewer of the 6 questions used in calculating Daily Activity Limitations score have missing item score, then the scale score is calculated by multiplying the mean of the non missing item score by 20. If 4 or more of the 6 item scores are missing then the scale score is not calculated and should be set at missing. Multiplying by 20 transforms the scale score to a 0 to 100 scale, with 0 reflecting the greatest degree of limitations on daily activities measurable by the scale and 100 reflecting the greatest freedom from limitations on daily activities.

1.b Feelings

| Feelings | Used in calculation of domain score? |
|------------------|--|
| 10. Irritability | Yes |
| | |

| Feelings | Used in calculation of domain score? |
|---|--|
| 11. Impatience | Yes |
| 12. Feeling sad | Yes |
| 13. Worry that my dry eyes will get worse | Yes |
| 14. Feeling annoyed | Yes |
| 15. Feeling like my eyes do not look nice | Yes |
| 16. Feeling like I have to make adjustments to my life | Yes |
| 17. Feeling different from other people because of my dry eyes | Yes |
| 18. Feeling like I am always aware of my eyes | Yes |
| 19. Feeling older than I really am | Yes |
| 20. Feeling like people look at me and think I am fine when I'm not | Yes |
| 21. Feeling like there is nothing I can do for my dry eyes | No |

| Response for questions 10 to 21 | Original response code | Item score |
|---------------------------------|------------------------------|------------|
| None of the time | 1 | 4 |
| A little of the time | 2 | 3 |
| Some of the time | 3 | 2 |
| Most of the time | 4 | 1 |
| All of the time | 5 | 0 |

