| 19. Sensitivity to recirculated air (such as air conditioning and | Yes |
| heat) | |
| 20. Headaches associated with dry eye symptoms | Yes |

| Response for question 1 | Original response code | Item score |
|-------------------------|---------------------------|------------|
| None of the time | 1 | 0 |
| A little of the time | 2 | 1 |
| Some of the time | 3 | 2 |
| Most of the time | 4 | 3 |
| All of the time | 5 | 4 |

| Response for questions 2 to 20 | Original response code | Item score |
|--|---------------------------|------------|
| I did not have this symptom / Not applicable | 6 | 0 |
| Not at all | 7 | 1 |

Confidential

Statistical Analysis Plan

Protocol: NGF0120

| Slightly | 8 | 2 |
|------------|----|---|
| Moderately | 9 | 3 |
| Very much | 10 | 4 |

All questions are included in the Symptom Bother scale score. If 50% (10) or fewer of the 20 questions used in the calculation of Symptom Bother scale score have missing item scores, then the scale score is calculated by multiplying the mean of the non missing item score by 25. If 11 or more of the 20 item scores are missing then the scale score is not calculated and should be set at missing. Multiplying by 25 transforms the scale score to a 0 to 100 scale, with 0 reflecting the greatest degree of treatment related bother measurable by the scale and 100 reflecting the lowest degree of treatment-related bother.

Change from baseline of above-defined subscores will be summarized as a continuous variable at each visit, and mean changes from baseline of all the subscores will be graphically presented (e.g. radar plot) for each visit.

• EQ-5D-5L change from baseline at week 4, 8, and week 32

Change from baseline of each dimension score and overall score of health today will be summarized as a continuous variable at each visit, and mean changes from baseline of all the dimension scores will be graphically presented (e.g. radar plot) for each visit.

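### SAP 5.2 scores IDEEL Symptom Bother so that 100 is the worst result, but its text says 100 is the best

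*SAP*

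**What the plan says.** SAP section 5.2 sets out the scoring of six IDEEL subscores. Module 3 is introduced as "Dry eye Symptom bother (20 questions) comprising a unique domain", and the scoring paragraph confirms that "All questions are included in the Symptom Bother scale score".

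- Question 1 (symptom frequency) runs from 0 for *none of the time* up to the row "All of the time | 5 | 4" (response label, data-entry code, item score).
- Questions 2 to 20 start at "I did not have this symptom / Not applicable | 6 | 0" and rise to an item score of 4 for *very much*.
- The scale score is the mean of the non-missing items times 25, provided no more than 10 of the 20 are missing.

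The paragraph ends by giving the meaning of the two ends of the scale: "with 0 reflecting the greatest degree of treatment related bother measurable by the scale and 100 reflecting the lowest degree of treatment-related bother".

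The same words close Module 2.b, where "3 questions are included in the Treatment-Related Bother scale score". There the item table is reversed: "None of the time | 1 | Missing | 4".

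**The concern.** The item tables and the direction sentence of Module 3 cannot both be right. Under the tables a higher score means more symptom bother; under the sentence it means less. The sentence also labels a symptom scale as treatment-related bother, so it needs editing whichever half is correct.

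Nothing else in the two documents settles it. SAP section 1.3.3.6 describes the questionnaire without giving a direction. The protocol lists IDEEL change as an endpoint (section 7.1.1) but gives no scoring. SAP section 10 cites the IDEEL user manual, but the SAP does not say that the manual prevails over its own scoring rules.

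At stake is the sign of the result for this subscore. The trial has one arm and no formal hypothesis test, so the mean change from baseline, with its confidence interval, is the whole finding, and no comparator would expose a reversed reading. Quality of life is named in the primary objective, and the protocol lists IDEEL among the quality-of-life questionnaires.

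**Working it through.** **Inputs (SAP section 5.2, Module 3).** Twenty items, each scored 0 to 4, all in the scale. Score = 25 × (sum of item scores) / (number of items answered).

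**Ends of the scale, all 20 items answered**

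- No symptoms on any item: 25 × (20 × 0)/20 = 0. The text calls this the greatest bother.
- Highest score on every item: 25 × (20 × 4)/20 = 100. The text calls this the lowest bother.

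**Between the ends**

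- *None of the time* on question 1 and *not at all* on the other 19: 25 × (0 + 19 × 1)/20 = 23.75.
- *Some of the time* and 19 × *slightly*: 25 × (2 + 19 × 2)/20 = 50.
- *Most of the time* and 19 × *moderately*: 25 × (3 + 19 × 3)/20 = 75.

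The score rises steadily with symptoms. One step on one item moves it by 25/20 = 1.25 points. Missing items do not alter the direction, because the mean of the remaining items behaves in the same way.

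**What would give the stated direction.** Replacing each item score by 4 minus the item score gives 0 for the worst pattern and 100 for the best. The SAP states no such step for Module 3. Where it reverses items elsewhere, it builds the reversal into the item-score table.

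**The other five subscores, same check**

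| Subscore | Worst answers | Best answers | Matches its own text? |
|---|---|---|---|
| 1.a Daily activities | 20 × 0 = 0 | 20 × 5 = 100 | Yes |
| 1.b Emotional well-being | 25 × 0 = 0 | 25 × 4 = 100 | Yes |
| 1.c Work | 25 × 0 = 0 | 25 × 4 = 100 | Yes |
| 2.a Treatment satisfaction | 25 × 0 = 0 | 25 × 4 = 100 | Yes |
| 2.b Treatment-related bother | 25 × 0 = 0 | 25 × 4 = 100 | Yes |
| 3 Symptom bother | 25 × 4 = 100 | 25 × 0 = 0 | **No** |

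For 1.a, for instance, the text gives "100 reflecting the greatest freedom from limitations on daily activities", and its item scores agree.

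**Effect on a change from baseline (assumed answers, not trial data)**

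- Baseline, *most of the time* and 19 × *moderately*: 75.
- Later, *a little of the time* and 19 × *slightly*: 25 × (1 + 19 × 2)/20 = 25 × 39/20 = 48.75.
- Change: 48.75 − 75 = −26.25. This is symptom relief, but the text reads it as worsening.
- Reversed score: 100 − 75 = 25 and 100 − 48.75 = 51.25, a change of +26.25.

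In general, reversal turns a mean change m with interval (L, U) into −m with interval (−U, −L).

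**The case against.** The strongest reply is that this is an editorial slip. The calculation is complete: item tables, number of items, missing-item rule and multiplier are all given, so a programmer obtains one value per patient. The direction sentence enters no derivation, cut-off or test. The scale's name and its item labels point to the right reading, and a sentence that repeats Module 2.b word for word, wrong construct included, looks like carried-over text. On that view nothing computed is wrong.

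Much of this stands. The wording does lean towards a carry-over, and the defect is an inconsistency between tables and text, not a wrong sum. It does not remove the problem. The sentence is the SAP's only explicit statement of direction for this subscore, and all five other subscores do run from worst at 0 to best at 100, so a missing reversal cannot be excluded from the documents alone. If the reversal is what is missing, the reported values change too.

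A second reply is that one subscore running against the others is not an error, since the SAP already reports EQ-5D-5L dimensions (high is worse) beside a health score on which high is better. That is fair: opposite direction is acceptable if it is stated. Table 14.2.7 and Figure 14.2.1 carry no direction in the text supplied. The mock shells are a separate document that was not available, so a note may exist there.

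**Conclusion.** The contradiction is real and exact: the two ends of the Symptom Bother scale are labelled the wrong way round for the score as defined. This rests on no assumption; only the 26.25-point illustration uses assumed answers.

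Which half is at fault cannot be decided without the IDEEL manual. If the tables are right, the values stand and their stated interpretation is reversed. Symptom Bother is then the only one of the six subscores on which a fall is an improvement, although all six are to be plotted together. If the text is right, every reported value and change must be reversed.

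The reach is limited to one subscore of a descriptive secondary variable in a study whose efficacy analyses are all declared exploratory. The primary healing endpoint, the sample size, EQ-5D-5L and the other five IDEEL subscores are unaffected. It should be fixed because it can reverse the reading of a patient-reported result.

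**What to change.** Before database lock, check the direction of the Symptom Bother score against the manual cited in SAP section 10, then make tables and text agree.

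- **If the manual has 100 as worst:** keep the item scores, change the sentence to state that 0 is the least and 100 the greatest symptom bother, and add a direction note to Table 14.2.7 and Figure 14.2.1. Reversing that axis of the radar plot is optional.
- **If the manual has 100 as best:** report 100 minus the computed score, and replace treatment-related bother with symptom bother in the sentence.

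The cost is one sentence plus a note on one table and one figure, or one line of derivation code plus the corrected label. No collected data change.

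As a query only, and not part of this finding: at the same check, confirm that question 1 is the intended gate for questions 8 to 10 in Module 2.b, and state what happens there when question 1 is missing.
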